The trial is a stepped-wedge cluster-randomized design clustered by homeless shelter. The intervention is implementation of on-site point-of-care molecular influenza testing and treatment with a single dose of baloxavir or a 5-day course of oseltamivir for all influenza-positive cases. Homeless shelters will be randomized to begin the intervention at different times throughout flu season. Residents within shelters will be eligible to participate if they have acute cough or two or more qualifying ARI symptoms (See **Table 1** for symptom list). The

control condition is an influenza-surveillance kiosk installed in a shelter that allows participants to collect a nasal swab that is then sent to an outside lab for testing. During the intervention period, symptomatic individuals with symptom onset in the last 48 hours will be eligible for point-of-care testing at a “improved” kiosk with a molecular test for influenza and an antiviral intervention if they have not yet received antiviral treatment for their symptoms. If they test positive for influenza, they will be administered an antiviral (either baloxavir or oseltamivir) when they receive their results. All participants will receive active drug; there will be no placebo arm. During the intervention period, symptomatic individuals with symptom onset in the last 3-7 days will be eligible to participate in swab collection, but will not receive point-of-care testing or antiviral treatment. Whole genome sequencing of all influenza-positive samples detected will enable the study team to determine whether a participant has acquired and transmitted the pathogen to secondary cases within-shelter, or whether a case represents a community-acquired infection.

Figure 1. Trial intervention schema

[figure not shown]

Primary outcome measure of the trial is number of cases of influenza per person-day in the shelter during the intervention period compared to the control period.

Secondary outcomes:

- Symptom duration and severity among cases
- Viral titer and shedding duration among cases
- Feasibility of implementation
- Cost effectiveness
- Emergence of viral resistance

Figure 2. Stepped wedge design for trial

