1. **Check eligibility:** Inclusion criteria specific to the intervention period that must be met prior to performing molecular testing include (1) ARI symptom onset within the past 48 hours and (2) not having already taken an antiviral for their current symptoms. Those

with acute cough or ≥ 2 ARI symptoms with onset between 3 and 7 days prior to enrollment are not eligible for molecular testing and antiviral treatment, but they should still complete the questionnaire and provide a nasal swab according to pre-intervention protocol. Additional inclusion and exclusion criteria can be found in section IV.

2. **Consent:** If the participant has had symptom onset within the past 48 hours, they must consent to the testing, antiviral dosage, and requisite follow-up procedures at this time. See *SFS Protocol* for additional details pertaining to non-intervention consent process.
3. **Questionnaire:** All participants must complete a REDCap survey that will ask questions gathering demographic, clinical and health behavior questions, and questions about prescription medications. This should take between 10-15 minutes to complete. After the participant has consented, the study staff member conducting the enrollment should ask whether they would prefer to complete the questionnaire themselves on the tablet or have them read the questions out loud to them and record their responses. Shelter clients may not be capable of completing the questionnaire alone if they do not have the appropriate corrective aids (glasses, contacts) for poor vision; are unfamiliar/uncomfortable with the technology and app; or have low English-language reading level. Kiosk staff should let the participant know that any question they are not comfortable providing information for they may skip and respond “Prefer not to say” in the app instead. Translated versions of the questionnaire will be available in Spanish, Tigrinya, and Amharic. We will submit translated consent forms prior to enrolling non-English speaking subjects. Telephonic translation services will also be available for participants who are not fully literate in English or their native language.
4. **Nasal swab:** One nasal swab will be collected from each participant. This singular nasal swab will both be tested on-site using the Abbott machine and will also provide a sample to be sent to the laboratory. See *SFS Protocol* for additional details pertaining to nasal swab collection procedures.

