15.1 kg to 23 kg	45 mg twice daily	7.5 mL	2 bottles	10 capsules (45 mg)
23.1 kg to 40 kg	60 mg twice daily	10 mL	2 bottles	20 capsules (30 mg)
40.1 kg or more	75 mg twice daily	12.5 mL	3 bottles	10 capsules (75 mg)

12. **Compensation:** All participants in both the surveillance and intervention component of this study will receive a \$5 gift card for their time (see *SFS Protocol*). Those that are eligible and enroll in the intervention component of this study will receive a \$30 gift card if tested positive and take an antiviral, with an additional \$5 gift card for each questionnaire and nasal swab that they provide during the 7-day follow-up period. The gift card ID will be logged in the REDCap application.

13. **Follow-up:**

- For any children up to age 5 who test positive for flu, we will recommend that they be seen by their pediatrician, or by an urgent care provider if they do not have a pediatrician, within 72 hours
- Research assistants will provide parents with a referral letter

- Travel vouchers will be provided for children to allow them and their caregivers to get to and from these appointments
- Following drug receipt, participants will have prospective questionnaire data and a nasal swab collected on day 2 or 3 and day 5, 6, or 7 after diagnosis. The participant will be required to return to the kiosk at their respective shelter on these days for the study staff to complete the questionnaire and provide a specimen. All participants will receive a \$30 gift card if tested positive and receive an antiviral, and an additional \$5 gift card for each subsequent nasal swab sample and symptom severity log that they provide on days 2/3 and 5/6/7, which will be logged in the REDCap application. A final follow-up questionnaire will be given on day 14 to assess for any adverse events. Any common treatment side effects experienced by the participant, which will have been shared by study staff during the consenting process, will be noted in the questionnaires during this follow up period alongside notes regarding relevant symptoms and their severity. These symptom logs will be used to monitor for the occurrence of adverse events (AEs) or serious adverse events (SAEs). See **Section XI** for additional detail about AE and SAE monitoring and reporting. (See **Appendix Additional File 2**).

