The shelter site coordinator will investigate data queries to provide an explanation and possible resolution of discrepancies on a daily basis using REDCap's data quality module overview. Site coordinator will raise queries and share them with the study staff who completed the respondent survey on site. The staff member will respond to the queries and mark the data item as "verified". Following additional review the manager will close the query. When there are no longer any open queries on a survey it can be locked by the site coordinator.

Full details on data management procedures are available in the *Data Management Plan*.

Intervention follow-up data collection

To follow up with enrolled influenza-positive individuals who received the study drug study staff will use a secondary REDCap survey app on the tablet with a built-in daily symptom log. The database will capture daily symptom responses recorded by the study staff member on day 2 or 3 and day 5, 6 or 7 following single-dose receipt of baloxavir and additional nasal swabs collected, as well as any adverse events experienced. These follow-up questionnaires will require retrospective recall of symptoms that the participant experienced every day following receipt of the study drug, not just days 3 and 7. This database will assign a study ID to each participant, linking nasal swabs collected and symptom log responses. Study staff are responsible for reviewing this database daily for each corresponding site once the intervention period has been introduced.

To contact enrolled participants to procure repeat swabs and symptom questionnaire responses, REDCap will automatically generate daily reports that provide study staff with the names and QR codes/unique links to the symptom logs of participants due for repeat swab collections that day. If they have one, participants will provide study staff with a cell phone

number to receive REDCap automated text messages to remind them when to return for follow-up sample collection. In addition, they will be given a paper appointment slip to remind them of when they are next due for a follow-up visit with study staff. Repeated swab collection on day 2 or 3 and 5, 6, or 7 will take place during the same hours and same location within each respective shelter to ensure participants are able to locate study staff for their follow-up appointments.

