Statistical analysis: Shelters will be analyzed with an intent to treat analysis to preserve the advantages of randomization. The number of influenza-positive tests will be analyzed using a generalized linear mixed model following a Poisson distribution with a log link and robust variance. The model is adjusted for calendar time and an exposure time variable based on shelter capacity. It will be used to calculate the relative risk of infection during the intervention period compared to prior to intervention, 95% confidence intervals, and p-value.

This model includes symptomatic individuals who tested throughout Year 1 of the study (November 15, 2019 – March 31, 2020).

Despite operational futility, descriptive statistics (counts, proportions, and appropriate measures of dispersion) for **both years 1 and 2** will be provided for the following Secondary Outcome Measures; additional statistical models will not be run due to low influenza case counts and the impact of the SARS-CoV-2 pandemic:

1. Feasibility of implementation of point-of-care molecular testing and treatment of influenza in shelters
 - a. Proportion of participant encounters with time between symptom onset until diagnosis with RT-PCR <48 hours in each study period
2. Feasibility of implementation of influenza treatment in shelters
 - a. Proportion of influenza-positive participants identified through on-site molecular testing in the intervention period that were treated with an antiviral
3. Proportion of participants that drop out of study
 - a. Measured as dropping out after providing consent
4. Proportion of participants that show non-compliance with study drug

- a. Only applicable to those that receive oseltamivir rather than baloxavir which is a single-dose antiviral. Measured based on self-report during follow-up visits with study research assistants.
5. Proportion of laboratory-confirmed influenza cases that report fever, or feverishness
 - a. Based on self-report, not gold standard measurement
6. Influenza viral RNA levels
 - a. Measured mean cycle threshold value for each laboratory-confirmed influenza-positive specimen collected at baseline enrollment
7. Proportion of samples with detectable influenza RNA virus at days 2/3 and days 5/6/7
 - a. Provided subject has not become lost to follow up

XI. Data Safety and Monitoring

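### Secondary outcome 7 (detectable RNA at follow-up) does not require a positive day-0 laboratory PCR, so on-site false positives can appear as viral clearance

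*Combined protocol and SAP*

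**What the plan says.** Who is followed up is decided on site. Section II says of people tested at the improved kiosk: "If they test positive for influenza, they will be administered an antiviral (either baloxavir or oseltamivir) when they receive their results". Section V (Follow-up) makes drug receipt the trigger for repeat swabs: "Following drug receipt, participants will have prospective questionnaire data and a nasal swab collected on day 2 or 3", with a second swab on day 5, 6 or 7. Section VIII describes the same group: "To follow up with enrolled influenza-positive individuals who received the study drug".

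What is measured is decided in the laboratory. Section VI sends the day-0 and follow-up swabs for RT-PCR. Section V, step 4, says the single day-0 swab "will both be tested on-site using the Abbott machine and will also provide a sample to be sent to the laboratory". Section VIII (Return of Results) puts the laboratory PCR result at about 7 days or more after swabbing.

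Three neighbouring items in the Section X list of secondary outcomes matter here:

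- Item 5: "Proportion of laboratory-confirmed influenza cases that report fever, or feverishness".
- Item 6: "Measured mean cycle threshold value for each laboratory-confirmed influenza-positive specimen collected at baseline enrollment".
- Item 7: "Proportion of samples with detectable influenza RNA virus at days 2/3 and days 5/6/7", with one condition: "Provided subject has not become lost to follow up".

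Section X plans descriptive statistics only for these outcomes, for both years, and cites low influenza case counts.

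**The concern.** Item 7 selects people with one assay and scores them with another, and does not require the two to agree at baseline. Someone whose on-site result was a false positive has no influenza RNA to clear. Their swabs at days 2/3 and 5/6/7 would be expected to be RNA-negative and would lower the detectable proportion exactly as real clearance does.

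Item 7 is the only post-treatment virological summary in Section X. Table 2 schedules follow-up swabs in the intervention period only, so no untreated series would reveal the problem. The false-positive share is also largest when influenza is scarce, which is the situation Section X describes.

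**Working it through.** **1. Can the protocol remove false positives before follow-up?** No. Drug is given when the on-site result is available, 15 to 30 minutes after swabbing (Section VIII, Return of Results). The laboratory result arrives at about day 7 or later, when both follow-up swabs are due or already taken. Any filter has to be applied at analysis.

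**2. Does the analysis text apply one?** Items 5 and 6 do; item 7 does not. Section II speaks of shedding among cases, and Section VI limits repeat swabs to flu-positive individuals, but neither names the test. Item 2 of the same list uses influenza-positive for people identified by on-site testing, so that term does not imply laboratory confirmation. No rule covers a swab that is positive on site and negative in the laboratory.

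**3. How large could the effect be?** The plan states no figure for item 7, so there is none to reproduce. The following is an illustration.

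Inputs from Section IV: a target population of 1,032, an effective control incidence of 1.6% per month, and at least 492 specimens per month. Implied positivity is 1,032 × 0.016 = 16.5 cases per month, and 16.5 / 492 = 3.4%. With the Section II maximum of 1,696 residents it is 27.1 / 492 = 5.5%. Both figures assume that every case is swabbed once. They are rough guides, because on-site testing is limited to symptom onset within 48 hours and positivity in that group is not given.

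Assumed, because the documents give no figures: sensitivity 95%; specificity 98% to 99.9%.

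False-positive share of on-site positives = (1 − p)(1 − spec) / [p × sens + (1 − p)(1 − spec)], where p is positivity among those tested.

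Example, p = 3.4% and specificity 99%: 0.966 × 0.01 / (0.034 × 0.95 + 0.966 × 0.01) = 0.00966 / 0.04196 = 23%.

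| Positivity among those tested | Spec. 99.9% | Spec. 99% | Spec. 98% |
|---|---|---|---|
| 0.5% (assumed, very low season) | 17% | 68% | 81% |
| 3.4% (planning figures) | 3% | 23% | 37% |
| 5.5% (planning figures, maximum census) | 2% | 15% | 27% |
| 10% (assumed) | 1% | 9% | 16% |
| 20% (assumed) | 0.4% | 4% | 8% |

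**4. Effect on the reported proportion.** If false positives stay RNA-negative, reported detection = true detection × (1 − false-positive share). At 3.4% positivity and specificities of 99.9%, 99% and 98%:

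- an assumed true 60% would be reported as about 58%, 46% and 38%;
- an assumed true 30% would be reported as about 29%, 23% and 19%.

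With the denominator limited to day-0 laboratory positives, this component of the error disappears.

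**The case against.** The strongest reply is that item 7 never defines its denominator. Section II frames the parent outcome as shedding among cases, and the primary outcome counts laboratory-confirmed cases, so an analyst might apply that restriction unprompted. The contrast with item 6 is also weak, since a cycle threshold exists only for a specimen that amplifies. This stands in part: the plan contains no explicit rule to count discordant participants as cleared. But item 5, on fever, has no such technical reason to say laboratory-confirmed and says it anyway, and item 2 shows that positive can mean positive on site. The text leaves the choice open, and its only stated condition does not exclude these participants.

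A second reply is that the bias may be trivial. The Background says rapid molecular tests match conventional RT-PCR in sensitivity and specificity, and at 99.9% specificity the share is only about 1% to 3% at 10% to 3.4% positivity. This stands as a limit on size. The statement gives no figure, however, and the same paragraph says performance in a low-resource community setting still has to be evaluated.

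Third, a discordant swab is not necessarily an on-site false positive. Some may be true low-load infections that the laboratory assay missed. This stands, and it is a reason to report the discordant group rather than drop it silently.

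A reader might also infer that the plan pools a normal season with a near-empty one, or that an estimated drug effect is contaminated. The documents support neither. Section X says that statistics will be given for both years, without saying whether they are combined, and item 7 has no untreated comparator from which a drug effect could be estimated.

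**Conclusion.** The gap is real. As written, item 7 admits participants selected by the on-site test with no baseline confirmation by the assay that defines the outcome. On-site false positives therefore push the detectable proportion down, towards apparent clearance.

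The size cannot be established from the documents. It ranges from negligible (specificity near 99.9% with positivity of 10% or more) to roughly a quarter to a third of on-site positives (specificity 98% to 99% at the 3.4% implied by the planning figures). These shares rest on the assumed sensitivity and specificity, and the effect on item 7 rests on false positives remaining RNA-negative at follow-up. A claim that the bias is known to be large would go beyond the evidence.

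The consequence is confined to one secondary, descriptive outcome. The primary outcome is defined on laboratory-confirmed cases and is unaffected. The correction is worth making because the direction of the error is predictable and the remedy is cheap.

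**What to change.** Amend item 7 in Section X as follows:

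- Restrict it to participants whose day-0 swab is influenza-positive by laboratory RT-PCR.
- Show the results by year.
- Report separately the number of on-site-positive, laboratory-negative participants and their follow-up PCR results, or include them in a sensitivity analysis.

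The cost is a few lines of text. The day-0 swab already goes to the laboratory, so no new samples or assays are needed, and because the restriction is made at analysis, nothing changes at the kiosk. The downsides are a smaller denominator in an outcome that already has few cases, and the exclusion of any true low-load infections that the laboratory assay missed. Reporting the discordant group covers the second. The change does not supply an untreated comparator, so item 7 would still describe viral detection after treatment without attributing it to the drug.
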